created for this project, on the same schedule as peer mentoring sessions. Both conditions will be delivered via Webex, which has several advantages for this intervention: 1) Sessions are easily accessible via phone or computer, allowing participants to choose their preferred interaction style; 2) A study coordinator can host the support groups and drop in/out for monitoring purposes; 3) There are video- or voice-call options for up to 25 participants at a time; and 4) This application ensures concordant delivery methods across both arms of the study and the ability to document the frequency that voice and video options are used to adjust for participant choices in analyses. All participants (mentees, mentors, and social support controls) will be assessed using validated measures of patient reported outcomes and clinical indicators of disease activity at baseline, mid-intervention (3 months from baseline), immediately post-intervention (6 months from baseline), and 6 months post-intervention (12 months from baseline). For each wave, outcomes for mentees randomized to the mentored group will be compared with the outcomes of mentees randomized to the support group. A booster session will be incorporated for all participants (mentored and support group) at 3 months post-intervention to encourage retention.[102]

B4c. Scientific Rigor: Assuming 3 post-randomization measurement time points, level of significance p=0.05, two-tailed comparison, correlation between pairs of measurements within participants (interclass correlation) no larger than p=0.7, AR(1) covariance structure, we estimate that 123 participants per group (total n=246) are needed to detect, with 80% power, a standardized effect size of 0.35sd with 20% inflation for attrition at 12 months. This study will apply strict principles of randomized clinical trials including randomization, blinding, careful tracking of all participants and intent-to-treat analyses to ensure robust and unbiased results.

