Power and Sample Size Justification: The sample size calculation and power analyses are based on the primary outcome of change in HRQOL between baseline and 12 months post intervention. The minimum sample size was based on detecting a clinically meaningful difference of 0.35 standard deviation units (medium effect) based on prior studies.[87,93,139-143] Essentially, this is equivalent to testing the interaction between time and group. Assuming 3 measurement time points, level of significance p=0.05, two-tailed comparison, correlation between pairs of measurements within participants (interclass correlation) no larger than p=0.6, compound symmetry covariance structure, we estimate that 123 participants per group (total n=246) are needed to detect, with 80% power, a standardized effect size of at least 0.35sd. This sample size includes a 20% inflation for attrition at 12 months. This effect size is robust enough to provide sufficient power for the outcomes listed under aims 1 and 2 and is consistent with data from our pilot study of 20 mentees and 7 mentors (see preliminary data). The pre-post differences in the outcomes (such as overall social support, positive social interaction, tangible support, vitality, emotional support, social functioning, general health, coping, etc), ranged from 0.35 to 0.88 standard deviation units. Although these calculations account for within patient clustering through the intera-class correlation mentioned above, clustering within mentors and mentees are assumed to have minimal intra-class correlation based on pilot data, especially since the cluster sizes would be at most 3 at a given wave. However, a multi-level model will be used in the analysis to verify this. Since the effect size planned is conservative, if the clustering leads to higher intra-class correlation, we would still be able to detect meaningful differences. We will also consider including mentor as a fixed effect in the model.

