AIM 1: Determine the efficacy of a peer mentorship intervention in African American women with SLE on disease self-management and HRQOL. Analyses for Aim 1 will focus on estimation of efficacy as determined by: (a) change in quality of life; and (b) change in self-management. Estimates of effect sizes for outcome variables will be reported as point estimates (mean differences between pre-post measures. as appropriate) and interval estimates (95% CI) with two-sided p-vales denoting statistical significance to provide an indication of the presence of a clinically important treatment effect. [145,146] A p-value of 0.05 will be considered to be statistically significant. After studying the distributions of baseline characteristics. we will use a generalized linear mixed model regression model to determine if the intervention will produce a greater change in the main outcomes from baseline. This model will include time, treatment (along with their interaction), and covariates (including the amount of intervention received, demographic factors, medications, coping, depression, stress, anxiety, health literacy, trust, and social support) as fixed-effects. Using the amount of intervention, which is measured as an aggregate number of sessions completed or hours of interaction as a covariate would allow us to study the dose response. In the generalized linear mixed model (GLMM), we will use different link functions depending on the assumed distribution of the response variable. For binary outcomes, we will use logit link and for count outcomes we will use log link under a poisson or negative binomial distribution. For example, for the a given quality of life variable, HRQOL measured at baseline, month 3 and month 6, we will include intervention group, time, and time X intervention as the primary independent variables in the basic (unadjusted) model, and covariates that are not balanced at randomization (or a propensity score based on these covariates) will be added in the subsequent (adjusted) model to adjust for the possible confounding effect of these variables. Unadjusted and covariate-adjusted least squares means for each outcome variable will be compared at the primary time point (month 12) and at intermediate secondary time point (month 6) using appropriate model contrasts and the Tukey-Kramer adjustment for multiple comparisons for the secondary time points. These contrast comparisons, along with corresponding 95% CI, will provide estimates of the difference in outcome means (effect sizes) for the hypothesized comparisons.

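### The Aim 1 efficacy model adjusts for attendance, which arises after randomisation, and the plan names no model or contrast as deciding efficacy

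*Combined protocol and SAP*

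**What the plan says.** All references are to the combined protocol and SAP.

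- **Overview of Statistical Analysis Plan, AIM 1, first model.** Efficacy is introduced as change in quality of life and in self-management. A generalized linear mixed model is to be used "to determine if the intervention will produce a greater change in the main outcomes from baseline". The next sentence reads: "This model will include time, treatment (along with their interaction), and covariates (including the amount of intervention received". The reason given is that using the "aggregate number of sessions completed or hours of interaction as a covariate would allow us to study the dose response".
- **Same paragraph, second description.** A basic model contains only group, time and their interaction. After it, "covariates that are not balanced at randomization (or a propensity score based on these covariates) will be added in the subsequent (adjusted) model".
- **Same paragraph, comparison.** "Unadjusted and covariate-adjusted least squares means for each outcome variable will be compared at the primary time point (month 12") and at month 6. These contrasts "will provide estimates of the difference in outcome means (effect sizes) for the hypothesized comparisons".
- **Power and Sample Size Justification.** The powered quantity is change in HRQOL from baseline to 12 months, and "this is equivalent to testing the interaction between time and group".
- **B4c. Scientific Rigor.** The study promises "careful tracking of all participants and intent-to-treat analyses to ensure robust and unbiased results".
- **Treatment Fidelity.** Sessions are counted in both arms, peer mentoring and support group alike.

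**The concern.** The paragraph leaves two things unsettled.

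First, attendance sits in the model that is meant to establish efficacy. It is a consequence of assignment and behaviour after randomisation. If one arm attends more, and women who attend more differ in prognosis, a difference in level adjusted for attendance mixes the treatment effect with that selection. It may also remove part of an effect that works through attendance. It is not the comparison promised in B4c.

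Second, several month-12 results would be available: unadjusted, adjusted for covariates chosen after imbalance is seen, adjusted for attendance, and each of these as a level or as a change from baseline. Nothing says which one answers Hypothesis 1. If they disagree, any of them could be presented as the efficacy result.

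**Working it through.** **1. The plan's own figure.** Take a two-sample comparison of change from baseline to month 12, two-sided 5%, 80% power, effect 0.35 SD and correlation 0.6 (Power and Sample Size Justification).

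- Variance of change = 2(1 − 0.6) = 0.8.
- n per group = 2 × ((1.960 + 0.842)/0.35)² × 0.8 = 128.1 × 0.8 = 102.5.
- With 20% inflation: 102.5 × 1.2 = 123.0. The stated figure is 123.

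So the unadjusted change contrast reproduces the stated sample size.

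**2. What attendance adjustment does to each contrast.** Suppose the model adds a term γ × D, where D is a woman's total sessions or hours, one value per woman.

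- *Change from baseline.* γD enters her baseline and month-12 values equally and cancels in the difference. With complete data the group × time contrast is therefore unchanged. The same holds for any baseline covariate entered as a main effect. A random-intercept fit to simulated complete data (four visits, 120 per arm) gave a month-12 change contrast of 0.2731 (SE 0.1127) with no covariate, with a baseline covariate and with attendance.
- *Level at month 12.* γD does not cancel. The estimate shifts by about −r × gap/SD, where r is the correlation of attendance with outcome, gap is the difference in mean sessions (mentored minus control) and SD is the spread of sessions.

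The documents give no attendance data, so any value of this shift is illustration only. Assuming r = 0.2, a 2-session gap and SD 3, the shift is 0.2 × 2/3 = 0.13. A true 0.35 becomes 0.22 if mentored women attend more, or 0.48 if controls do. With r from 0.1 to 0.3 and gaps of 1 to 3 sessions, the shift runs from 0.1 × 1/3 = 0.03 to 0.3 × 3/3 = 0.30 SD in either direction. With equal attendance it is zero. SD 3 is also too wide for retained mentored women. Under the rule on missed sessions they would have 9 to 12 sessions (emergency absences aside), so their SD could not exceed 1.5.

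**3. Level against change, with no attendance assumption.** Inputs: 0.35 SD and correlation 0.6 as above, and 150 per arm (B4b. Study Overview) less 20% = 120 completers per arm.

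- SE of level = √(2/120) = 0.129; z = 0.35/0.129 = 2.71; power 77%.
- SE of change = √(2/120 × 0.8) = 0.115; z = 0.35/0.115 = 3.03; power 86%.
- Correlation of the two test statistics = (1 − 0.6)/√0.8 = 0.447.

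From the bivariate normal distribution:

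| | 120 per arm | 98 per arm (123 less 20%) |
|---|---|---|
| Power, level | 77% | 69% |
| Power, change | 86% | 78% |
| Tests disagree, true effect 0.35 | 23% | 29% |
| At least one rejects, no effect | 9.2% | 9.2% |

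These figures size the choice between level and change. They do not size the choice between adjusted and unadjusted models. For the change contrast with complete data and main-effect covariates, that choice makes no difference (step 2).

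**The case against.** The strongest reply is that the plan already points to a safe contrast. AIM 1 opens by defining efficacy as change, its model tests change, and the sample size rests on the time-by-group interaction. Step 2 shows that a single attendance term does not bias that contrast when data are complete. The sentence on least squares means also follows directly after the two models that contain no attendance term, and the stated purpose of attendance is dose response. All of this stands, and it limits the point.

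It does not close it. The plan never confines the least squares means to those two models, and "covariate-adjusted" fits the first model equally well. The sample-size section justifies a number and does not select a model. For Aim 2 the plan places covariate adjustment in a second set of analyses, but it says nothing equivalent for Aim 1. Complete data cannot be assumed either, since 20% attrition is planned for.

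A reader might infer that attendance adjustment biases the trial's primary result. The documents do not support that. Bias requires the adjusted level difference to be used (or missing data, or covariate-by-time terms, which the plan does not specify), together with attendance that differs by arm and is prognostic.

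It can also be said that fixing change as the deciding contrast is partly preference: at the same inputs a baseline-adjusted month-12 comparison has SE √(2/120 × 0.64) = 0.103 and 92% power. That is fair. The need is for one contrast to be named; change is proposed because it is the one the plan powers.

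**Conclusion.** The point holds in limited form and should be fixed. A post-randomisation variable is in the model described as determining efficacy, and neither a model nor a contrast is named as deciding.

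The part that can be sized without inventing attendance data is level against change: 77% against 86% power, disagreement in 23% of trials at a true 0.35 SD, and 9.2% instead of 5% null rejection if either result may be claimed. This rests on the plan's correlation of 0.6, equal variances at baseline and month 12, and 120 completers per arm. The harm from attendance adjustment is conditional, and its size and direction are unknown.

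A reader might also infer that removing attendance leaves an intent-to-treat analysis. It does not by itself. The Randomization Procedure admits a woman to the intent-to-treat analysis only once she has attended the first session, and the Recruitment and enrollment text under the PALS intervention has mentees dropped for missed sessions. The analysis set is a separate question.

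**What to change.** In the AIM 1 analysis text:

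1. Remove amount of intervention received from the efficacy model and give dose response its own analysis, labelled exploratory.
2. Name as primary the model with group, time and group × time, plus only baseline covariates listed in advance, if any.
3. Name as its deciding contrast the month-12 between-group difference in change from baseline, which is the quantity the sample size is built on.
4. Label all other comparisons supportive, including those adjusted for observed imbalance or a propensity score.
5. As a clarification, state that medications and the psychosocial covariates enter at their baseline values.

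The cost is SAP wording. Sample size and data collection do not change, and the dose-response question is still answered. The change frees the deciding contrast from attendance adjustment. The first-session condition and the rule on missed sessions still have to be reconciled with the intent-to-treat promise separately.

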
AIM 2: Determine the impact of a peer mentorship intervention in African American women with SLE on clinical indicators of disease activity and clinical profile that indicates success of the intervention. Analyses for Aim 2 will focus on estimation of efficacy as determined by: change in disease activity of ≥4 point reduction from baseline in SLEDAI score, in concordance with the accepted SLE Responder Index (SRI).[147] For comparative statistical assessments, the two groups will be compared using a generalized linear mixed models (GLMM) approach.[148] This approach allows for measurement of participants at different time points, missing data under the assumption of missing at random (MAR), and can also account for the effect of correlated longitudinal measurements within participants. In addition, GLMM accommodates a wide range of distributional assumptions such as dichotomous (e.g. binomial), count (e.g. Poisson), continuous (e.g. Gaussian), and categorical or ordinal outcomes. Additionally, outcomes that are measured longitudinally (at 6 and 12 months) will have intervention group, time, and time-by-intervention group as primary independent variables in the model. Additional adjustment covariables will be added to the model in a second set of analyses, when indicated. The magnitude of between intervention differences in outcome variables (effect sizes) at each time point will be estimated using appropriate contrasts in the corresponding GLMM models. We will then perform a responder analysis to develop a profile of the clinical and laboratory characteristics that predict success of the intervention. For this, a multivariate regression logistic regression model where the outcome is success (/failure) and the difference in the clinical (SLEDAI components) levels over time are independent variables. We will use model selection approaches such as the all subsets selection, to identify the important clinical and laboratory features in the presence of others. As much as the data allows, we will also consider interactions of the SLEDAI components. As an alternative to logistic regression, we will also consider other approaches such as the CART, or logic forest to efficiently identify the clinical and laboratory characteristics that predict intervention success.

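### Aim 1 has two conflicting covariate rules, one of which selects on chance imbalance, and names no primary model for the month-12 comparison

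*Combined protocol and SAP*

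**What the plan says.** All of this is in the Overview of Statistical Analysis Plan.

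- **Fixed list (Aim 1).** The mixed model is to contain time, treatment, their interaction and "covariates (including the amount of intervention received, demographic factors, medications, coping, depression, stress, anxiety, health literacy, trust, and social support) as fixed-effects".
- **Imbalance rule (Aim 1).** Later in the same paragraph, in a worked example for quality of life, a basic model holds only group, time and their interaction. Then "covariates that are not balanced at randomization (or a propensity score based on these covariates) will be added in the subsequent (adjusted) model", with the purpose given as "to adjust for the possible confounding effect of these variables". No p-value, standardised difference or other criterion defines imbalance.
- **What the models feed.** "Unadjusted and covariate-adjusted least squares means for each outcome variable will be compared at the primary time point (month 12". Neither version is named as primary.
- **Aim 2.** "Additional adjustment covariables will be added to the model in a second set of analyses, when indicated". No criterion is given here either.

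The protocol also has a list of covariates for all three aims, which includes the lupus damage index (BILD). The Power and Sample Size Justification paragraph sizes the trial on the time-by-group interaction.

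**The concern.** Participants are randomised individually, so a baseline imbalance is chance and not confounding in the usual sense. Choosing covariates because they look imbalanced makes the adjusted model depend on the draw. It passes over predictors that happen to be balanced, which is where most of the precision gain lies, and the reported standard errors take no account of the selection. A propensity score built from the same covariates inherits the problem.

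The fixed list does not cure this. It contradicts the imbalance rule, and it contains a variable that arises after randomisation and can itself be affected by the assigned arm, so it cannot serve unchanged as the adjustment set. With two rules, no criterion and no primary model, more than one month-12 estimate could be presented as the result.

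**Working it through.** **Plan's own figure.** Inputs from the Power and Sample Size Justification paragraph: "level of significance p=0.05, two-tailed comparison", 80% power, 0.35 SD, correlation 0.6 under compound symmetry, 20% attrition inflation. For a change score:

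n = 2 × (1.960 + 0.842)² × 2(1 − 0.6) / 0.35² = 2 × 7.849 × 0.8 / 0.1225 = 102.5 per arm; × 1.2 = 123.0.

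This reproduces the stated 123 per group. The documents give no figure for covariate adjustment itself.

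**Completers assumed.** 0.8 × 123 ≈ 98 per arm. From planned enrolment, 0.8 × 150 = 120 per arm.

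**Month-12 between-group contrast.** With complete data and a free mean for each arm at each visit, the unadjusted contrast is the raw difference at month 12, even though baseline is among the responses. In SD units:

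- SE without adjustment = √(2/n)
- SE with one prespecified covariate of correlation r ≈ √(2/n) × √(1 − r²)
- Power ≈ Φ(0.35/SE − 1.96)

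The imbalance rule was simulated with one covariate, entered only if its balance test gave p < 0.05.

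| Per arm | r | SE, none | SE, fixed | Power, none | Power, imbalance rule | Power, fixed |
|---|---|---|---|---|---|---|
| 98 | 0.3 | 0.143 | 0.136 | 69% | 69% | 73% |
| 98 | 0.6 | 0.143 | 0.114 | 69% | 69% | 86% |
| 120 | 0.3 | 0.129 | 0.123 | 77% | 77% | 81% |
| 120 | 0.6 | 0.129 | 0.103 | 77% | 78% | 92% |

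Repeat runs moved the imbalance-rule figures by up to two points.

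**Choice of r.** The documents give correlations only for repeated measures of the outcome, as upper bounds: 0.6 (compound symmetry, power paragraph) and 0.7 (AR(1), Scientific Rigor paragraph). If baseline and months 3, 6 and 12 are successive AR(1) steps, the baseline to month-12 value is at most 0.7³ = 0.34. No value is given for age, wave or BILD.

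**Several covariates.** A second simulation used four visits, a random intercept (0.6), 98 completers per arm, and 1 or 10 covariates jointly explaining a share R² of outcome variance. Imbalance was taken as p < 0.05, p < 0.10 or a standardised difference above 0.2. These settings are assumptions.

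| R² | Model SE, imbalance rule | Model SE, fixed | Power, imbalance rule | Power, fixed |
|---|---|---|---|---|
| 0.1 | 0.142–0.143 | 0.136–0.138 | 68–70% | 71–74% |
| 0.3 | 0.139–0.143 | 0.120–0.121 | 70–73% | 82–85% |
| 0.5 | 0.137–0.142 | 0.101–0.102 | 70–75% | 93–94% |

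With no covariates the SE was 0.143 and power 67–71%.

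**Error bars.** Type I error under the imbalance rule ran from 2.7% to 5.1%. In the most extreme case (R² 0.5, ten covariates, standardised difference above 0.2) the reported SE was 0.138 against an actual SD of 0.122, and 95% intervals covered 97.3%.

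**How often the rule fires.** With independent covariates tested at 0.05, the chance that at least one looks imbalanced is 1 − 0.95¹⁰ = 40% for ten and 1 − 0.95¹³ = 49% for thirteen.

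**Time-by-group interaction.** In one simulated complete data set, adding a baseline main effect left the interaction at 0.2380 (SE 0.1283). The SE of the month-12 least-squares-mean difference fell from 0.145 to 0.123.

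**The case against.** The strongest reply is that the trial is sized on change from baseline, through the time-by-group interaction, and with complete data no baseline main effect alters that contrast. At correlation 0.6 its power is Φ(0.35/(0.894 × 0.143) − 1.96) ≈ 78% with 98 per arm and about 86% with 120, whatever the covariate rule. This stands. The loss applies only if the month-12 comparison of least-squares means is read as a between-group difference at that visit. The plan's text supports that reading too, and does not choose.

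It is also fair that the imbalance rule sits in an example, that a fixed list precedes it, and that the unadjusted result is to be reported alongside. A reader might infer that strong predictors will certainly be left out. The documents do not establish that; they establish two incompatible rules.

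A reader might also infer inflated false positives. Applied mechanically, the rule errs in the conservative direction. With no criterion, mechanical application is not assured, but analyst discretion was not simulated and no size can be put on it.

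Finally, a reader might take the Aim 2 sentence as the same imbalance rule. It states no rule, and its stated endpoint is a binary SLEDAI response, to which the linear results above do not carry over.

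**Conclusion.** The point holds as a defect of specification with a cost in precision. For the month-12 between-group contrast, the imbalance rule performs almost like no adjustment. The power forgone, relative to prespecified adjustment, is about 4 points at correlation 0.3 and about 14 to 17 points at 0.6, for a 0.35 SD effect and 98 to 120 completers per arm. Weak covariates make it a small matter; a strong one, plausibly the baseline outcome, does not. The intervals are too wide rather than too narrow. These sizes rest on assumed correlations and imbalance thresholds. Nothing here shows that 123 per group is wrong for the interaction on which it was computed. The conflict between the two lists, the post-randomisation covariate and the missing primary model need no assumption: they follow from the text.

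**What to change.** - Delete the imbalance rule and the propensity-score option.
- Name one primary model for the month-12 contrast. Give it a short list of baseline-only covariates, fixed before arm-level data are seen and entered whatever the balance: baseline value of the outcome, wave, age and baseline BILD. All are already planned data.
- Use the baseline outcome once. Either model post-baseline visits only with baseline as a covariate, or keep baseline among the responses with arm means constrained equal at baseline, but not both.
- Remove quantity of intervention from the efficacy model and place it in a separate exploratory dose-response analysis.
- For Aim 2, replace the open-ended wording with the same list. For the binary SLEDAI response, state that the adjusted odds ratio is conditional on the covariates, or report a standardised risk difference.

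The cost is SAP wording, with no added participants, visits or measurements. The downside is that the list and the primary model must be fixed in advance and cannot respond to imbalances seen later.

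### The plan describes two different month-12 contrasts, arm means and change from baseline, and neither makes efficient use of the outcome's own baseline score

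*Combined protocol and SAP*

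**What the plan says.** The Aim 1 text of the Overview of Statistical Analysis Plan contains two descriptions of the efficacy comparison.

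- **Month-12 means.** The sentence that names the primary time point reads "Unadjusted and covariate-adjusted least squares means for each outcome variable will be compared at the primary time point (month 12"). Its model is described in a worked example for one quality-of-life outcome: "we will include intervention group, time, and time X intervention as the primary independent variables in the basic (unadjusted) model". The example's responses are the baseline, 3-month and 6-month scores, so baseline is one of the responses. Nothing sets the two arms' baseline means equal.
- **Change.** The opening of the same text defines efficacy by change in quality of life and in self-management, and says the model is to show a greater change from baseline.

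The Power and Sample Size Justification takes the second view. Its calculation is "based on the primary outcome of change in HRQOL between baseline and 12 months post intervention", and it adds: "Essentially, this is equivalent to testing the interaction between time and group".

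On adjustment, the listed covariates do not include the outcome's own baseline value. The adjusted model adds covariates found unbalanced at randomisation, or a propensity score built from them.

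**The concern.** A participant's baseline PAM or LUP-QOL score is likely to be among the best predictors of her month-12 score, and it is collected on everyone. How it enters the model decides how much of that information is used.

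- In a model with a free mean for every arm and visit, comparing month-12 means ignores baseline. A chance difference between the arms at baseline then passes in part into the result.
- Comparing change subtracts the whole baseline difference. That is too much unless the correlation is 1, and it adds noise when the correlation is low.

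The two contrasts have different standard errors and can give different p-values. The plan does not say which one is the primary test. Power is at stake, as is a choice of contrast left open until data are in hand.

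**Working it through.** **Inputs.** From the Power and Sample Size Justification: "level of significance p=0.05, two-tailed comparison"; 80% power; a difference of 0.35 SD; correlation "no larger than p=0.6, compound symmetry covariance structure"; a 20% inflation for attrition; 123 per group. From B4c, Scientific Rigor: AR(1) with correlation up to 0.7. From the Recruitment Strategy: 150 per arm. The 0.35 SD is assumed to be in units of the SD of the outcome score.

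**Variance factors.** Let r be the baseline to month-12 correlation. Relative to the raw month-12 difference, with complete data, the contrast variances are:
- month-12 means with free baseline means: 1
- change from baseline: 2(1 − r)
- baseline-adjusted: 1 − r²

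The adjusted factor is never the largest: 1 − r² ≤ 1, and 2(1 − r) − (1 − r²) = (1 − r)² ≥ 0. The change factor exceeds 1 when r < 0.5.

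**The plan's own figure.** n per arm = 2(1.960 + 0.842)²/0.35² × factor = 128.14 × factor. With r = 0.6:
- change: 128.14 × 0.80 = 102.5; × 1.2 = 123.0, which matches 123
- month-12 means: 128.14 × 1.00 = 128.1; × 1.2 = 153.8
- baseline-adjusted: 128.14 × 0.64 = 82.0; × 1.2 = 98.4

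Of the contrasts tried on that section's inputs, only change gives 123. The AR(1) inputs of B4c come within 3% in two other ways (120.7 and 121.7, dividing by 0.8), but not with change (156.9 or more).

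**Does the month-12 means contrast ignore baseline?** Generalised least squares on four visits gives a variance ratio to the raw month-12 difference of 1.000, under both compound symmetry 0.6 and AR(1) 0.7. A common baseline mean lowers it to 0.64 and 0.88. With 20% dropout, likelihood estimation with free means recovers about 2% to 9% of the variance from earlier visits.

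**Power.** Two-sample noncentral t, effect 0.35/√factor, 150 × 0.8 = 120 completers per arm. The value 0.343 is 0.7³, AR(1) over the three intervals from baseline to month 12.

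| r | Factors (means, change, adjusted) | Power |
|---|---|---|
| 0.6 | 1.00, 0.80, 0.64 | 77.0%, 85.5%, 92.1% |
| 0.343 | 1.00, 1.314, 0.882 | 77.0%, 65.4%, 82.0% |

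Over r = 0.3 to 0.7, the change contrast runs from 62.6% to 93.6% and the adjusted one from 80.8% to 96.6%.

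**Chance imbalance.** The SD of the baseline difference at 150 per arm is √(2/150) = 0.115 SD. An imbalance of that size shifts the contrasts as follows:
- month-12 means, by r × 0.115: 0.069 SD at r = 0.6 (20% of 0.35) and 0.040 SD at 0.343 (11%)
- change, in the opposite direction, by (1 − r) × 0.115: 0.046 SD at 0.6 (13%) and 0.076 SD at 0.343 (22%)

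**The case against.** A reader might infer that the trial's only deciding analysis throws the baseline score away. The documents do not support that. They also state change and the time-by-group interaction, and the sample size matches change. For that contrast at correlation 0.6, baseline lowers the variance by 20%.

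Other points on the plan's side:

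- **The model is not fully specified.** The plan does not say that time is categorical, and the sentence with baseline among the responses is an example that stops at month 6. Equality with the raw difference is therefore conditional on categorical time and free arm means. This stands, and it is also a reason to specify the model.
- **Imbalance is partly addressed.** Adjusted means are planned too, with covariates such as depression and coping that may correlate with the outcome. They may remove part of an imbalance. The plan does not say that the outcome's own baseline is among them.
- **The 0.6 figures are favourable.** It is stated as an upper limit. At 0.343 the gain over month-12 means is about 5 percentage points of power (77% to 82%).
- **Bias.** A reader might take the imbalance shift as bias, or add it to the power loss. Neither is right: it is conditional imbalance already included in the standard error, and the contrast is unbiased over randomisation.
- **Common-baseline models need care here.** The Randomization Procedure enters a woman into the intent-to-treat analysis only after she attends a first session. The first session differs by arm, so baseline means among those analysed need not be equal in expectation. This stands, and it determines which fix is preferred.

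**Conclusion.** The point holds in this form: two month-12 contrasts are described, none is named as primary, and baseline adjustment is at least as precise as either at every correlation. Against month-12 means, the gain is from 77% to 92% power at correlation 0.6 and from 77% to 82% at 0.343. Against change, it is from 86% to 92% and from 65% to 82%. The month-12 means contrast stays below the planned 80% on completers even with 150 enrolled per arm.

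These figures assume 0.35 SD on the outcome scale, 20% loss, completers only and no mentor clustering. Likelihood estimation would narrow the gap slightly. The claim that baseline adds no precision applies only to the month-12 means contrast, with categorical visit, free baseline means and complete data. The change should be made, but its absence would not invalidate the trial.

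**What to change.** In the Aim 1 analysis text, name one primary month-12 contrast for PAM and LUP-QOL. Fit the scores at months 3, 6 and 12 as outcomes, with categorical visit, group, group-by-visit, and the outcome's own baseline score by visit as a covariate. Include that covariate whether or not it looks imbalanced, and take the month-12 arm difference from this model. Align the wording on change and interaction in the Power and Sample Size Justification with it.

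A longitudinal model with a common baseline mean is an equivalent option if all randomised women are analysed. The baseline-covariate version does not need equal baseline means among first-session attenders.

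Use the same approach for continuous SLAQ and SLEDAI scores. The Aim 2 responder endpoint, a SLEDAI reduction of at least 4 points, already uses baseline and is outside this point.

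The cost is SAP wording, settled before outcome data are compared by arm. No new data are needed.
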